13.2.7 Record Retention

The investigator will maintain all study records according to current ICH E6 GCP Guidelines and/or applicable local regulatory requirement(s), whichever is longest, as described in the Clinical Trial Agreement. If the investigator withdraws from the responsibility of keeping the

study records, custody will be transferred to a person willing to accept the responsibility and Vertex will be notified.

13.2.8 Study Termination

At any time, Vertex may terminate this study in its entirety or may terminate this study at any particular site. In addition, for reasonable cause, either the investigators or their IRBs/IECs may terminate the study at their center.

Conditions that may lead to reasonable cause and warrant termination include, but are not limited to:

- Subject or investigator noncompliance
- Unsatisfactory subject enrollment
- Lack of adherence to protocol procedures
- Lack of evaluable and/or complete data
- Potentially unacceptable risk to study subjects
- Decision to modify drug development plan
- Decision by the FDA or other regulatory authority

Written notification that includes the reason for the clinical study termination is required.

13.2.9 End of Study

The end of study is defined as the last scheduled visit (or scheduled contact) of the last subject.

13.3 Data Quality Assurance

Vertex or its designated representative will conduct a study site visit to verify the qualifications of each investigator, inspect clinical study site facilities, and inform the investigator of responsibilities and procedures for ensuring adequate and correct study documentation per current ICH E6 GCP Guidelines.

The investigator is required to prepare and maintain adequate and accurate case histories designed to record all observations and other data pertinent to the study for each subject. Study data for each enrolled subject will be entered into a CRF by study site personnel using a secure, validated, web-based electronic data capture (EDC) application. Vertex will have read-only access to site-entered clinical data in the EDC application.

Instances of missing, discrepant, or uninterpretable data will be queried with the investigator for resolution. Any changes to study data will be made to the CRF and documented in an audit trail, which will be maintained within the clinical database.

13.4 Monitoring

Monitoring and auditing procedures developed or approved by Vertex will be followed to comply with GCP Guidelines. Checking of the CRFs/SAE Forms for completeness and clarity, cross-checking with source documents, and clarification of administrative matters will be performed.

The study will be monitored by Vertex or its designee. Monitoring will be done by a representative of Vertex or designee (study site monitor), who will review the CRFs/SAE Forms and source documents per current ICH E6 GCP Guidelines. The study site monitor will ensure that the investigation is conducted according to the protocol design and regulatory requirements.

13.5 Electronic Data Capture

Vertex will provide the study sites with secure access to and training on the EDC and decentralized trial platform applications sufficient to permit study site personnel to enter or correct information in the CRFs on the subjects for which they are responsible.

A CRF will be completed for each enrolled study subject. It is the investigator's responsibility to ensure the accuracy, completeness, clarity, and timeliness of the data reported in the subject's CRF. Source documentation supporting the CRF data will indicate the subject's participation in the study and will document the dates and details of study procedures, AEs, other observations, and subject status.

The investigator, or designated representative, will complete the CRF as soon as possible after information is collected.

The audit trail entry will show the user's identification information and the date and time of any correction. The investigator will provide formal approval of all the information in the CRFs, including any changes made to them, to endorse the final submitted data for the subjects for whom the investigator is responsible.

Vertex will retain the CRF data and corresponding audit trails. A copy of the final archival CRF in the form of a compact disc (CD) or other electronic media will be placed in the investigator's study file.

Sites will use an EDC tool to record data for each enrolled subject. Additionally, subjects will use the decentralized trial platform to record electronic activity and cough diary, [REDACTED] which will be considered the source for that data.

It is the investigator's responsibility to ensure the accuracy, completeness, clarity, and timeliness of the data reported. The investigator is required to prepare and maintain adequate and accurate case histories designed to record all observations and other data pertinent to the study for each subject, including the dates and details of study procedures, AEs, other observations, and subject status.

The audit trail entry will show the user's identification information and the date and time of any correction. The investigator will provide formal approval of all data reported to Vertex, including any changes made, to endorse the final submitted data for the subjects for whom the investigator is responsible.

[figure not shown]

13.7 Publications and Clinical Study Report

13.7.2 Clinical Study Report

A clinical study report (CSR), written in accordance with the current ICH E3 Guideline, will be submitted in accordance with local regulations.

APPENDIX A Eligible MF *CFTR* Mutations

“MF” mutations are a subset of minimal function mutations that are non-responsive to IVA and TEZ/IVA. A mutation is considered an MF mutation if it meets at least 1 of the following 2 criteria:

- (1) No biological plausibility of translated protein (genetic sequence predicts the complete absence of CFTR protein), or
- (2) in vitro testing that supports lack of responsiveness to IVA and TEZ/IVA.

Inclusion of MF Mutations Based on In Vitro Testing

Mutations that were considered to be MF mutations based on in vitro testing met the following criteria in in vitro experiments:

- baseline chloride transport that was <10% of wildtype CFTR
- an increase in chloride transport of <10% over baseline following the addition of IVA and TEZ/IVA in the assay

Eligible MF Mutations

The mutations below are detectable by an FDA-cleared genotyping assay or other method (e.g., sequencing).

This list does not include every eligible mutation, and investigators should contact the medical monitor regarding other mutations that may also meet study eligibility criteria.

Non-exhaustive List of Minimal Function *CFTR* Mutations Eligible for VX20-445-126

Q2X	L218X	Q525X	R792X	E1104X
S4X	Q220X	G542X	E822X	W1145X
W19X	Y275X	G550X	W882X	R1158X
G27X	C276X	Q552X	W846X	R1162X
Q39X	Q290X	R553X	Y849X	S1196X
W57X	G330X	E585X	R851X	W1204X
E60X	W401X	G673X	Q890X	L1254X
R75X	Q414X	Q685X	S912X	S1255X
L88X	S434X	R709X	Y913X	W1282X
E92X	S466X	K710X	Q1042X	Q1313X
Q98X	S489X	Q715X	W1089X	Q1330X
Y122X	Q493X	L732X	Y1092X	E1371X
E193X	W496X	R764X	W1098X	Q1382X
W216X	C524X	R785X	R1102X	Q1411X
185+1G>T	711+5G>A	1717-8G>A	2622+1G>A	3121-1G>A
296+1G>A	712-1G>T	1717-1G>A	2790-1G>C	3500-2A>G
296+1G>T	1248+1G>A	1811+1G>C	3040G>C (G970R)	3600+2insT
405+1G>A	1249-1G>A	1811+1.6kbA>G		3850-1G>A
405+3A>C	1341+1G>A	1811+1643G>T	3120G>A	4005+1G>A
406-1G>A	1525-2A>G	1812-1G>A	3120+1G>A	4374+1G>T
621+1G>T	1525-1G>A	1898+1G>A	3121-2A>G	
711+1G>T		1898+1G>C		
182delT	1119delA	1782delA	2732insA	3791delC
306insA	1138insG	1824delA	2869insG	3821delT
365-366insT	1154insTC	1833delT	2896insAG	3876delA
394delTT	1161delC	2043delG	2942insT	3878delG
442delA	1213delT	2143delT	2957delT	3905insT
444delA	1259insA	2183AA>G ^a	3007delG	4016insT
457TAT>G	1288insTA	2184delA	3028delA	4021dupT
541delC	1343delG	2184insA	3171delC	4022insT
574delA	1471delA	2307insA	3171insC	4040delA
663delT	1497delGG	2347delG	3271delGG	4279insA
849delG	1548delG	2585delT	3349insT	4326delTC
935delA	1609del CA	2594delGT	3659delC	
1078delT	1677delTA	2711delT	3737delA	

Non-exhaustive List of Minimal Function *CFTR* Mutations Eligible for VX20-445-126

CFTRdele1	CFTRdele16-17b		991del5
CFTRdele2	CFTRdele17a,17b		1461ins4
CFTRdele2,3	CFTRdele17a-18		1924del7
CFTRdele2-4	CFTRdele19		2055del9>A
CFTRdele3-10,14b-16	CFTRdele19-21		2105-2117del13insAGAAA
CFTRdele4-7	CFTRdele21		2372del8
CFTRdele4-11	CFTRdele22-24		2721del11
CFTR50kdel	CFTRdele22,23		2991del32
CFTRdup6b-10	124del23bp		3121-977_3499+248del2515
CFTRdele11	306delTAGA		3667ins4
CFTRdele13,14a	602del14		4010del4
CFTRdele14b-17b	852del22		4209TGTT>AA
A46D	V520F	Y569D	N1303K
G85E	A559T	L1065P	
R347P	R560T	R1066C	
L467P	R560S	L1077P	
I507del	A561E	M1101K	

CFTR: cystic fibrosis transmembrane conductance regulator gene

Source: CFTR2.org. Clinical and functional translation of CFTR. The Clinical and Functional Translation of CFTR (CFTR2), US Cystic Fibrosis Foundation, Johns Hopkins University, the Hospital for Sick Children. Available at: <http://www.cftr2.org>. Accessed 15 February 2016.

^a Also known as 2183delAA>G.

4 INTRODUCTION

Study VX20-445-126 (Study 445-126) is a Phase 3b open-label study evaluating the efficacy of elexacaftor (ELX, VX-445) in triple combination (TC) with tezacaftor (TEZ) and ivacaftor (IVA) on cough and physical activity using wearable devices in subjects 12 years of age (inclusive) and older with cystic fibrosis (CF) who are heterozygous for *F508del* and a minimal function mutation (F/MF).

This statistical analysis plan (SAP) is based on the most recent approved clinical study protocol (CSP), the most recent approved electronic case report form (eCRF), and the most recent approved eCRF completion guidelines.

This SAP (Methods) documents the planned statistical analyses of efficacy and [REDACTED] defined in the VX20-445-126 study protocol. It also documents analyses for additional efficacy and safety variables not specified in the protocol, which will provide supportive information for the scientific understanding of the drug entity.

The Vertex Biometrics Department will perform the statistical analysis of efficacy and [REDACTED]; SAS (Version 9.4 or higher) will be used to generate all statistical outputs (tables, figures, listings, and datasets). The SAP will be finalized and approved prior to the clinical database lock. Any revisions to the approved SAP will be documented and approved in an amendment to the SAP.

5 STUDY OBJECTIVES

To evaluate the effects of ELX/TEZ/IVA on cough and physical activity using wearable technology

[figure not shown]
6 STUDY ENDPOINTS

6.1 Primary Endpoint

- Percent reduction from baseline in cough frequency (cough events per day) to the average of Week 8 through Week 12

6.2 Secondary Endpoint

- Absolute change from baseline in total step count per day to the average of Week 8 through Week 12

[figure not shown]

7 STUDY DESIGN

7.1 Overall Design

This is a Phase 3b, open-label study evaluating the effects of ELX/TEZ/IVA on cough and physical activity using wearable technology. A schematic of the study design is shown in Figure 7-1. All subjects will receive ELX 200 mg once daily (qd)/TEZ 100 mg qd/IVA 150 mg every 12 hours (q12h) for approximately 13 weeks. A treatment duration of approximately 13 weeks allows the efficacy endpoints to be collected with wearable devices through Week 12 (i.e. a complete, 24-hour cough assessment during Week 12 and at least 12 complete weeks of continuous actigraphy measures in the treatment period). The Week 13 clinic visit is for operational purposes, at which patients return the wearable devices and complete any in-clinic assessments. Approximately 100 subjects will be enrolled.

Figure 7-1 VX20-445-126 Study Design

ELX: elexacaftor; IVA: ivacaftor; N: total sample size; TEZ: tezacaftor

Notes: Subjects who are eligible will be offered the opportunity to enroll in an open-label extension safety study evaluating ELX/TEZ/IVA. The Safety Follow-up Visit is not required for subjects who complete the Week 13 Visit and have enrolled in the open-label extension study, or who transition to a commercially available CFTR modulator regimen, within 28 days

7.2 Sample Size and Power

The primary efficacy endpoint is percent reduction from baseline in cough frequency (cough events per day) to the average of Week 8 through Week 12. Assuming a standard deviation of 1 for the log ratio of cough frequency post-baseline versus baseline, a sample size of approximately 100 subjects will provide 95% confidence intervals (which represents the estimation precision) as shown in Table 7-1 at various observed percent reductions in cough frequency (30%, 40%, and 50%), after accounting for 20% missing. Note: percent reduction equals $100\% \times (1 - \text{ratio of cough frequency post-baseline vs. baseline})$.

Table 7-1 95% Confidence Intervals for Percent Reduction in Cough Frequency per day from Baseline

Percent reduction in cough frequency	30%	40%	50%
95% Confidence Intervals	(13%, 44%)	(25%, 52%)	(38%, 60%)

30%, 40%, 50% percent reduction corresponds to ratio of 0.7, 0.6 and 0.5 in cough frequency (post-baseline vs. baseline), respectively.

8 ANALYSIS SETS

The following analysis sets are defined: All Subjects Set, Full Analysis Set (FAS) and Safety Set.

8.1 All Subjects Set

The **All Subjects Set** will include all subjects who were enrolled. This analysis set will be used for all individual subject data listings and disposition summary tables, unless otherwise specified.

8.2 Full Analysis Set

The **Full Analysis Set (FAS)** is defined as all enrolled subjects who carry the intended *CFTR* allele mutation and have received at least 1 dose of study drug. The FAS is to be used in efficacy analyses.

8.3 Safety Set

The **Safety Set** is defined as all subjects who have received at least 1 dose of study drug. The Safety Set is to be used for all safety analyses.

9 STATISTICAL ANALYSIS

9.1 General Considerations

Continuous variables will be summarized using the following descriptive summary statistics: the number of subjects (n), mean, SD, median, minimum value (min), and maximum value (max).

Categorical variables will be summarized using counts and percentages.

Baseline value, unless specified otherwise, will be defined as the most recent non-missing measurement (scheduled or unscheduled) collected before the first dose of study drug.

Absolute change from baseline will be calculated as post-baseline value – baseline value.

Relative change from baseline will be calculated and expressed in percentage as $100\% \times (\text{post-baseline value} - \text{baseline value}) / \text{baseline value}$.

Treatment-emergent (TE) Period will include the time from the first dose of study drug to 28 days after the last dose of study drug or to the completion of study participation, whichever occurs first.

Incomplete/missing data will not be imputed, unless specified otherwise.

Unscheduled visits: Unscheduled visit measurements will be included in analysis as follows:

- 1) In scheduled visit windows per specified visit windowing rules
- 2) In the derivation of baseline and last on-treatment measurements
- 3) In the derivation of maximum and minimum values during TE period, and maximum and minimum change from baseline values during TE period for safety analyses
- 4) In individual subject data listings as appropriate

Visit windowing rules: The analysis visit windows for protocol-defined visits are provided in Appendix A.

Outliers: No formal statistical analyses will be performed to detect or remedy the presence of statistical outliers, unless specified otherwise.

9.2 Background Characteristics

9.2.1 Subject Disposition

The number and percentage (based on All Subjects set) of subjects in each of the following disposition categories will be summarized:

- Enrolled

- Completed study drug treatment
- Prematurely discontinued treatment (i.e., discontinued all study drugs) and the reason for discontinuation
- Completed study
- Prematurely discontinued the study and the reason for discontinuation
- Rollover to the open-label study

A listing will be provided for subjects who discontinued treatment or who discontinued study with reasons for discontinuation.

9.2.2 Demographics and Baseline Characteristics

Demographics and baseline characteristics will be summarized based on the FAS.

Demographic data will include the following:

- Age at baseline (in years)
- Sex (female and male)
- Ethnicity (Hispanic or Latino, not Hispanic or Latino, and not collected per local regulations)
- Race (White, Black or African American, Asian, American Indian or Alaska Native, Native Hawaiian or Other Pacific Islander, Other, and not collected per local regulations)
- Country

Baseline characteristics will include the following:

- Weight (kg)
- Height (cm)
- BMI (kg/m²)

Disease characteristics will include the following:

- ppFEV₁ at baseline (<30, ≥30 to <40, ≥40 to <70, ≥70 to ≤90, and >90)
- ppFEV₁ at baseline (continuous)
- Prior use of dornase alfa (Yes, No)
- Prior use of azithromycin (Yes, No)
- Prior use of inhaled antibiotic (Yes, No)
- Prior use of bronchodilator (Yes, No)
- Prior use of inhaled bronchodilator (Yes, No)
- Prior use of inhaled hypertonic saline (Yes, No)
- Prior use of inhaled corticosteroids (Yes, No)

In addition, data listings will also be provided for:

- Informed consent;
- Inclusion/Exclusion criteria violation for subjects with any such violations.

The predicted FEV₁ will be calculated using the Global Lung Function Initiative (GLI)¹; details are provided in Appendix B.

9.2.3 Medical History

Medical history will be coded by using the Medical Dictionary for Regulatory Activities (MedDRA). Medical history will be summarized descriptively by System Organ Class (SOC) and Preferred Term (PT) for the FAS. The corresponding data listing will also be provided.

9.2.4 Prior and Concomitant Medications

Medications will be coded using the World Health Organization Drug Dictionary (WHO-DD) and categorized as follows:

- **Prior medication:** any medication that administered during the 56 days before the first dose of study drug.
- **Concomitant medication:** medication continued or newly received during the TE period.
- **Post-treatment medication:** medication continued or newly received after the corresponding TE period.

A given medication may be classified as a prior medication, a concomitant medication, or a post treatment medication; both prior and concomitant; both concomitant and post treatment; or prior, concomitant, and post treatment.

If a medication has a missing or partially missing start/end date or time and if it cannot be determined whether it was taken before the first dose of study drug, concomitantly during the TE Period, or after the TE Period, it will be considered in all 3 categories of prior, concomitant, and post treatment medication. Details for imputing missing or partial start and/or stop dates of medication are described in Appendix C.

Prior medications and concomitant medications during the Treatment Period will be summarized descriptively for the FAS using frequency tables by: 1) preferred name (PN); and 2) anatomic class (ATC) level 1, ATC level 2, and PN.

The number of subjects who used hormonal therapy concomitantly during the Treatment Period will be summarized based on the Safety Set.

9.2.5 Study Drug Exposure

Study drug exposure will be summarized based on the Safety Set.

Duration of study drug exposure (in weeks) will be calculated as: (last dose date of study drug – first dose date of study drug + 1)/7, regardless of study drug interruption.

Study drug exposure in weeks will be summarized descriptively by the number of subjects (n), mean, SD, median, min, and max. It will also be summarized by intervals using counts and percentages.

9.2.6 Study Drug Compliance

Study drug compliance will be summarized based on the FAS.

Study drug compliance will be calculated as: $100 \times [1 - (\text{total number of days of study drug interruption}) / (\text{duration of study drug exposure in days})]$. A study drug interruption on a given day is defined as an interruption of any study drugs on that day. A study drug interruption that continues through the end of the study participation (i.e., subject does not resume study drug before the end of the study participation) will not be included in the compliance calculation.

Study drug compliance will be summarized descriptively by the number of subjects (n), mean, SD, median, min, and max. It will also be summarized in categories: <80% and \geq 80% using frequency tables.

9.2.7 Important Protocol Deviations

An important protocol deviation (IPD) is a deviation that may significantly affect the completeness, accuracy, or reliability of the study data or that may significantly affect a subject's rights, safety, or well-being. A protocol deviation review team will categorize IPDs according to the Protocol Deviation Plan during the study.

IPDs will be summarized descriptively based on the FAS. Additionally, IPDs will be provided in an individual subject data listing.

9.3 Efficacy Analysis

Unless otherwise defined, all efficacy analyses described in this section will be based on the FAS.

9.3.1 Analysis of Primary Efficacy Variable

9.3.1.1 Definition of Variable

The primary endpoint is percent reduction from baseline in cough frequency (cough events per day) to the average of Week 8 through Week 12. Percent reduction from baseline will be calculated and expressed in percentage as $100\% \times (\text{baseline value} - \text{post-baseline value}) / \text{baseline value}$ (i.e., -relative change)

Cough frequency per day will be measured by a non-invasive, semi-automated, ambulatory cough monitoring system. The device will be used for a single day (defined by 24 continuous hours) at visits specified in Table 3-2 in CSP. The 24-hour assessment is considered valid if there are at least 10 cumulative hours of recording duration while awake, excluding any duration where the recording is identified as muted, flagged, or device not attached, and excluding any duration where the recording ended early.² For valid assessments, the cough frequency per day is the total number of cough events in the 24-hour period (excluding any duration where the recording is identified as muted, flagged, or device not attached, and excluding any duration where the recording ended early).

The baseline value is defined as the geometric mean of valid cough measurements prior to the first dose of study drug (e.g., Day -14 and Day -7). If one value is missing or invalid, the non-missing, valid value will be used. If the cough frequency is zero at a given visit, 0.5 will be added to ensure a non-zero number.

9.3.1.2 Primary Analysis

The primary endpoint is the percent reduction from baseline in cough frequency (cough events per day) to the average of Week 8 through Week 12. The primary analysis will be based on a mixed-effects model for repeated measures (MMRM) with change from baseline at each post-baseline visit (Week 2 to Week 12) on the natural log scale (i.e., $\log(\text{post-baseline}) - \log(\text{baseline})$) as the dependent variable. Note that if cough frequency is zero at any visit, 0.5 will be added in order to ensure a non-zero number for appropriate natural log calculations. The model will include visit as a fixed effect and log baseline cough frequency as a covariate. The model will be estimated using restricted maximum likelihood. Denominator degrees of freedom for the F-test for fixed effects will be estimated using the Kenward-Roger approximation.³ An unstructured covariance structure will be used to model the within-subject errors. If the model estimation does not converge, a compound symmetry covariance structure will be used instead. Conditional on the observed data and covariates, missing data will be assumed to be missing at random; no additional imputation of missing data will be performed.

The primary result obtained from the model will be the estimated percent reduction in cough frequency from baseline to the average of Week 8 through Week 12 (defined as the average of Weeks 8, 9, 10, 11, 12). Percent reduction will be calculated as $100\% \times (1 - \text{exponential form of LS mean change at the average of Weeks 8 through 12 on the natural log scale from the above MMRM model})$. The 2-sided 95% confidence intervals will be provided. Furthermore, the estimated percent reduction at each post-baseline week will also be provided. The estimated percent reduction at each post-baseline week up to Week 12 will be plotted.

The geometric mean and geometric SD of the raw values at baseline and each post-baseline visit up to Week 12 will also be summarized. In addition, daytime and overnight cough frequency per hour will be summarized in a similar way. If the daytime or overnight cough frequency per hour is zero at a given visit, 0.5/24 will be added to ensure a non-zero number.

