12.3.3 Efficacy Analysis

12.3.3.1 Analysis of Primary Endpoint

The primary endpoint is percent reduction from baseline in cough frequency (cough events per day) to the average of Week 8 through Week 12. The primary analysis will be based on a mixed-effects model for repeated measures (MMRM) with change from baseline at each post-baseline visit on the natural log scale as the dependent variable. The model will include week as fixed effects and baseline cough frequency as covariate.

The primary result obtained from the model will be the estimated percent reduction in cough frequency from baseline to the average of Week 8 through Week 12, i.e., $100\% \times (1 - \text{exponential form of LS mean change estimate from the above MMRM model})$. The 2-sided 95% confidence intervals will be provided. Furthermore, the estimated percent reduction at each post-baseline week will also be provided.

Additional details will be provided in the SAP.

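### The primary 95% CI treats log baseline as fixed, so as an interval for the population geometric mean ratio it is too narrow whenever log change depends on log baseline

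*SAP*

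**What the plan says.** The study has one arm: "All subjects will receive ELX 200 mg once daily (qd)/TEZ 100 mg qd/IVA 150 mg every 12 hours (q12h) for approximately 13 weeks" (SAP 7.1).

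The primary model (SAP 9.3.1.2) is an MMRM of log post-baseline minus log baseline at Weeks 2 to 12, fitted by REML with Kenward-Roger degrees of freedom. On covariates it says: "The model will include visit as a fixed effect and log baseline cough frequency as a covariate". Protocol 12.3.3.1 plans the same structure: "The model will include week as fixed effects and baseline cough frequency as covariate". The reported result is 1 minus the "exponential form of LS mean change at the average of Weeks 8 through 12 on the natural log scale", with a two-sided 95% CI. Neither document says at which baseline value the LS mean is taken, or whether the interval refers to the population or only to the baselines observed.

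On the baseline itself, SAP 9.3.1.1 says: "The baseline value is defined as the geometric mean of valid cough measurements prior to the first dose of study drug". Two single-day recordings are scheduled, and "If one value is missing or invalid, the non-missing, valid value will be used".

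Precision is planned in SAP 7.2 and Protocol 12.1: "Assuming a standard deviation of 1 for the log ratio of cough frequency post-baseline versus baseline", with about 100 subjects and 20% missing. Tables 7-1 and 12-1 give intervals of (13%, 44%), (25%, 52%) and (38%, 60%) for reductions of 30%, 40% and 50%.

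**The concern.** In a randomised comparison, the sampling error of the mean baseline largely cancels between arms. Here it does not. The LS mean change is itself the result, and if change depends on baseline, a different sample of patients would have a different mean baseline and so a different mean change. The model standard error ignores that source of variation. Kenward-Roger does not restore it, because it allows for estimating the covariance parameters and not for a random covariate mean.

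Some dependence is plausible. Log baseline is subtracted in the response and is also the covariate, and it rests on at most two scheduled days of recording. If the effect is unrelated to true baseline, noise in the measured baseline alone produces a negative slope.

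The stake is the stated precision. The sample size is justified only by interval width, and the public text describes no test or comparator for the primary endpoint. The CI is therefore its only inferential statement of uncertainty.

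**Working it through.** **Inputs from the documents:** SD of the log ratio 1; 100 subjects with 20% missing, so n = 80; two-sided 95%, z = 1.96 (SAP 7.2 and 9.3.1.2). **Assumed:** LS mean at the sample mean log baseline; ρ, the correlation of log change with log baseline, which neither document gives.

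**1. Reproduce the plan's table.** Limits are 1 − (1 − p) × exp(±1.96 × 1/√80), with 1/√80 = 0.1118.

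| Reduction p | Computed | Tables 7-1 and 12-1 |
|---|---|---|
| 30% | (12.9%, 43.8%) | (13%, 44%) |
| 40% | (25.3%, 51.8%) | (25%, 52%) |
| 50% | (37.8%, 59.8%) | (38%, 60%) |

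The table uses the full SD of the log ratio, not a residual SD after adjustment for baseline.

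**2. Compare the two variances.** With complete data, the LS mean at the sample mean log baseline equals the mean log ratio.
- Sampling variance around the population value: residual variance/n + slope² × Var(log baseline)/n = SD²/n.
- Variance in the model standard error: residual variance/n = SD² × (1 − ρ²)/n.
- Ratio of standard errors: √(1 − ρ²). Coverage for the population value: 2Φ(1.96 × √(1 − ρ²)) − 1.

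**3. Results over assumed ρ (SD 1, n = 80, 40% reduction).**

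| Assumed \|ρ\| | SE ratio | Coverage | Interval printed by the model | Widening needed, 1/√(1 − ρ²) − 1 |
|---|---|---|---|---|
| 0 | 1.000 | 95.0% | (25.3%, 51.8%) | 0% |
| 0.3 | 0.954 | 93.8% | (26.1%, 51.3%) | 4.8% |
| 0.5 | 0.866 | 91.0% | (27.5%, 50.4%) | 15.5% |
| 0.6 | 0.800 | 88.3% | (28.5%, 49.6%) | 25.0% |

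A complete-data simulation (baseline-adjusted regression, n = 80) at ρ = −0.5 gave 91.3% coverage for the population value, 95.1% with the omitted term added, and 95.0% for the mean at the sample's own mean baseline.

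**4. The planned model with drop-out and Kenward-Roger.** The simulation had 11 visits, unstructured covariance, 100 enrolled, missing-at-random drop-out, and a mean of 97 subjects contributing. Baseline and follow-up were given a correlation of 0.5 and equal log SDs, which implies ρ = −0.5. The mean Kenward-Roger standard error was 0.0910 against an empirical SD of 0.1048. Coverage was 91.5%, and 95.2% with the added term (standard error 0.1045).

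**5. Baseline noise alone.** Assume the effect is independent of true baseline, with between-subject log SD st of 0.7 to 1.3, day-to-day log SD sw of 0.4 to 0.8, and m baseline recordings. Then |ρ| = (sw²/m)/√(st² + sw²/m).
- Worst corner with m = 2 (st = 0.7, sw = 0.8): 0.32/√(0.49 + 0.32) = 0.356, coverage 93.3%.
- Best corner with m = 2 (st = 1.3, sw = 0.4): 0.08/√(1.69 + 0.08) = 0.060, coverage 95.0%.
- The median over an even grid of these ranges is about 94.7%.
- If every subject had only one recording, the range would be 88.2% to 94.8%. The SAP allows a single recording only as a per-subject fallback.

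**6. Step count.** SAP 9.3.2.2 has the same structure without the log. One simulated case (12 weekly intervals, assumed correlation 0.7, equal SDs) gave 93.3%, and 95.2% with the term added.

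**The case against.** The strongest reply is that this is a standard baseline-adjusted MMRM whose interval is correct for what it conditions on, and that neither document names a population target. That stands. A reader might infer that the interval is simply wrong; the documents do not support that, since coverage is nominal for the mean at the observed baselines. The fault is an undeclared target. The population reading rests on SAP 7.2, whose precision figures use the full variance of the log ratio.

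A reader might also infer that coverage will be about 88% to 91%. The documents do not support that either: they give no correlation or slope, and in the noise-only case with two recordings the loss is slight.

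A realised interval narrower than Table 7-1 is not in itself an error. The table assumes 80 subjects, and more may contribute to the MMRM. In the simulation above even the corrected standard error (0.1045) was below the table's 0.1118.

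With complete data, the unadjusted mean log ratio also gives nominal coverage. It is simpler, but it gives up the model's handling of incomplete follow-up under missing at random. For step count, SAP 9.3.2.2 already reports the SD of change at each weekly interval, so unadjusted weekly precision can be seen there.

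**Conclusion.** The point holds as a matter of stated precision. If the population geometric mean ratio is the target and the LS mean is taken at the sample mean log baseline, the planned CI is too narrow by the factor √(1 − ρ²). There is no shortfall at ρ = 0, and its size in this trial cannot be known from the documents. The point estimate is essentially unchanged, and no test, success threshold or interim decision depends on the interval. It is worth fixing before database lock because this CI is the only inferential statement of uncertainty for the primary endpoint and the correction is cheap. Confidence is medium, because both the target and the evaluation point have to be inferred.

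**What to change.** Keep the MMRM. In SAP 9.3.1.2:

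1. State that the target is 1 minus the population geometric mean ratio of cough frequency, average of Weeks 8 to 12 against baseline.
2. State that LS means are evaluated at the mean log baseline of the FAS subjects who contribute to the model, one value per subject.
3. Compute the primary 95% CI from variance(LS mean) + (estimated slope)² × s²(log baseline)/n, with n those same subjects and the model's Kenward-Roger degrees of freedom, then back-transform.

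Apply the same term to the step-count LS mean change in SAP 9.3.2.2, where the target is the population mean change. If an interval conditional on the observed baselines is intended instead, say so and state that it is not comparable with Table 7-1.

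The cost is SAP wording and a few lines of code, with no new data. The CI widens as in the last column of the table above, and hardly at all if the slope is near zero. The correction is approximate if the baseline slope differs by visit: simulated coverage moved from 92.6% to 93.9% when the slope of follow-up on baseline fell over visits, and from 95.3% to 96.3% when it rose. A subject-level bootstrap that refits the model is an optional check; it was not tested here.
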